6.5 LOCAL LABORATORY ASSESSMENTS

- CBC with differential

6.6 MECHANISTIC ASSESSMENTS

- IgE [UniCAP™] to peanut
- Basophil activation assay
- Cellular assays
- Plasma assays
- Stool and saliva assays
- HLA

6.7 STUDY VISITS

6.7.1 Screening

6.7.1.1 Study Visit -2

See Appendix 1 for detailed assessments.

6.7.1.2 Visit -1

Participants who meet visit -2 eligibility criteria may return for visit -1 to undergo an initial blinded OFC of 500 mg peanut protein. Visit -2 and visit -1 procedures may occur on the same day. See Appendix 1 for detailed assessments.

6.7.2 Initial Dose Escalation - Study Visit 0

The initial dose escalation will occur on a single day at the clinical research center. Peanut or placebo dosing will begin with 0.2 mg peanut flour extract (0.1 mg peanut protein) or placebo flour extract with graduated doses every 15-30 minutes up to 12 mg peanut flour (6 mg peanut protein) or placebo flour, if tolerated, in one day. A table listing dose increments during initial dose escalation is in [Section 3.1](#).

Participants will not have active wheezing or a current flare in atopic dermatitis. If symptoms occur preventing escalation to 12 mg peanut flour (6 mg peanut protein) or placebo flour, the highest tolerated dose of at least 3 mg peanut flour (1.5 mg peanut protein) or placebo flour will be accepted as the dose for further escalation. Participants must tolerate at least 3 mg peanut flour (1.5 mg peanut protein) or placebo flour as a final dose to remain in the study.

Intravenous access will be established prior to initial day of dosing and maintained with a saline/heparin lock, per investigator's discretion. Intramuscular epinephrine will be available. If necessary, albuterol will be used for lower respiratory symptoms (wheezing). A licensed and qualified nurse coordinator will oversee administration of the dose to the participant. A physician is required to be available on site during administration and must be available at all times for emergency treatment for anaphylaxis.

Since the participants are very young children, they may have clear liquids, JELL-O, or other small amounts of food such as crackers, cereal, etc. during the day of the initial dose escalation while they are being given the desensitization doses.

Participants may develop symptoms during the initial escalation. The investigator's judgment will be required to determine the best course of action with possible actions being:

1. Extend time interval between dosing (up to an additional 30 minutes).
2. Return to previously tolerated dose (i.e., repeat of last tolerated dose) then advance forward.
3. Discontinue protocol.

For *oral or pharyngeal pruritus*, the action should be to continue the normal dosing in 30 minutes.

For *mild symptoms*, defined as:

- skin — limited or localized hives or swelling, skin flushing or pruritus
- respiratory — rhinorrhea or sneezing, nasal congestion, occasional cough, throat discomfort
- GI — mild abdominal discomfort or minor episode of vomiting

the action should be either to repeat the last dose in 30-60 minutes or to advance in 30-60 minutes depending on the physician's discretion.

For *moderate symptoms*, defined as:

- skin — systemic hives or swelling
- respiratory — throat tightness without hoarseness, persistent cough, wheezing without dyspnea

- GI — persistent moderate abdominal pain/cramping/nausea, increased vomiting

the action should be to implement a 30-60 minute observation period and if symptoms resolve, reduce the dose by one step, repeat the same dose, or increase the dose by one step;

if symptoms continue or worsen, the participant can be treated with appropriate rescue medication:

if symptoms resolve, reduce the dose by one step, repeat the same dose, or increase the dose by one step;

if symptoms require additional treatment, then consultation with the Protocol Chair or Co-Chair as listed on the cover page of the protocol is warranted to determine the next course of action. The Protocol Chair or Co-Chair will be available for questions and decision making for any questions related to the study protocol from 10 AM ET to 5 PM ET Monday through Friday.

For *severe symptoms*, defined as:

- respiratory — laryngeal edema, throat tightness with hoarseness, wheezing with dyspnea
- GI — significant severe abdominal pain/cramping/repetitive vomiting
- neurological — change in mental status
- circulatory — hypotension

The initial escalation dose should be discontinued and the appropriate rescue medications administered.

If the subject requires treatment for symptoms with antihistamines on one occasion during the initial escalation protocol, then the rest of the protocol may be followed. If the subject requires more than one medication (e.g., albuterol, diphenhydramine, epinephrine, or others) or multiple doses of antihistamines, the initial escalation protocol should be terminated.

For a completed initial escalation protocol with no symptoms or only mild symptoms, subjects should have a 2-hour post-protocol observation period. For moderate to severe symptoms, the observation period should be at least 4 hours, and up to 24 hours, based on symptoms and treatment regimen needed to stabilize.

[figure not shown]

Figure 2 Management of Symptoms during Initial Dose Escalation

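### Section 6.7.2 gives two unreconciled instructions for a child with moderate symptoms who receives more than one rescue medication, or repeat antihistamine, during initial dose escalation

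*Combined protocol and SAP*

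**What the plan says.** Section 6.7.2 sorts reactions on the initial escalation day by symptom grade. For moderate symptoms there is first an observation period. After that:

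- "if symptoms continue or worsen, the participant can be treated with appropriate rescue medication". No type or number of drugs is specified beyond that.
- After that treatment, "if symptoms resolve, reduce the dose by one step, repeat the same dose, or increase the dose by one step".
- Otherwise, "if symptoms require additional treatment, then consultation with the Protocol Chair or Co-Chair" "is warranted to determine the next course of action".

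Severe symptoms have their own instruction: stop the escalation and treat.

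A separate paragraph follows all the grades and refers to none of them. It allows a child to go on after treatment with "antihistamines on one occasion during the initial escalation protocol, then the rest of the protocol may be followed". It then says that if the child "requires more than one medication (e.g., albuterol, diphenhydramine, epinephrine, or others) or multiple doses of antihistamines, the initial escalation protocol should be terminated".

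Earlier in the section, a child who cannot reach 6 mg protein keeps the highest tolerated dose, provided it is at least 1.5 mg protein. That dose "or placebo flour will be accepted as the dose for further escalation". Section 5.2 ends allergen therapy for a child who does not reach 1.5 mg protein.

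**The concern.** The moderate-symptom branch and the medication paragraph cover the same children but lead to different actions and different decision-makers. One leaves open a further dose, possibly a higher one, or refers the decision to the Chair or Co-Chair. The other ends escalation and mentions neither grade nor consultation. A site team with a child who has just been treated can follow either paragraph and be compliant with the text.

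Safety is the main stake: the choice decides whether that child receives more allergen the same day. Two further consequences follow. The point at which escalation stops sets the highest tolerated dose, and so the Table 1 column in which build-up starts. It can also decide whether the 1.5 mg threshold is met, and so whether the child stays on therapy. Appendix 1 places randomization at this same visit, so a child removed here already belongs to the ITT sample of Section 9.1.

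**Working it through.** The plan states no figure for this rule, so the check is a comparison of the two instructions on cases that the protocol itself foresees. Section 5.3.3 expects that antihistamine, epinephrine, albuterol and other drugs may be combined for one reaction. Section 6.7.2 classes both systemic hives and wheezing without dyspnea as moderate, and names albuterol for wheezing.

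1. **Moderate reaction, one antihistamine dose, then a second drug or a second antihistamine dose is needed.** Branch: consult, outcome open. Medication paragraph: terminate. The instructions differ.
2. **Moderate reaction treated at once with two rescue drugs; symptoms resolve.** Branch: lower, repeat or raise the dose one step. Medication paragraph: terminate. They differ, and the branch permits a higher dose directly.
3. **Two separate moderate reactions, each resolving after one antihistamine dose.** Branch: after the second, the dose may again be lowered, repeated or raised. Medication paragraph: terminate, because antihistamine was given more than once. They differ.
4. **Moderate reaction treated with a single non-antihistamine drug; symptoms resolve.** Branch: the dose may be lowered, repeated or raised. Medication paragraph: neither clears the child nor terminates. This is a gap, not a contradiction.

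The medication paragraph cannot be only a restatement of the severe-symptom rule. Severe symptoms already lead to discontinuation, and the paragraph's first sentence lets a treated child continue. It must therefore reach non-severe reactions.

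**Start column (Table 1, mg protein).** The columns start build-up at 6, 3 and 1.5 mg. The ratios are 6/1.5 = 4, 6/3 = 2 and 3/1.5 = 2. On schedule the columns reach 2000 mg at weeks 24, 26 and 28, so the largest delay is 28 − 24 = 4 weeks in a 134-week course. All three are at 2000 mg when maintenance begins at week 30.

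**Route to the primary analysis.** Section 9.2.2 counts any randomized subject without an evaluable blinded OFC as a failure. Section 9.3 plans 96 children in the treatment arm. Each such child who was removed at this step, had no evaluable OFC and would otherwise have passed lowers that arm's observed pass proportion by 1/96 ≈ 1.0 percentage point. How many children that would be cannot be derived, because the documents give no frequency for treated reactions on this day.

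**The case against.** The strongest reply is that the medication paragraph, placed after all the symptom grades, is an overall cap on them. That reading is plausible. It even leaves the consultation something to decide: a repeat dose of one non-antihistamine drug falls outside the cap, and the next course of action may concern care other than escalation. But the text does not say that it is a cap, and for a second drug or repeat antihistamine the consultation would then have little left to decide about escalation.

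Investigator judgment is also invoked in Section 6.7.2, with stopping among the options. That covers the single-drug gap in case 4. It does not settle cases 1 to 3, where one paragraph directs termination and the other does not. Figure 2 deals with symptom management on this day and may set the order of the rules. Since it is not shown, one cannot say that the conflict stands whatever the figure contains.

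A reader might infer more than the documents support:

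- *That a child needing additional treatment goes straight to a higher dose under the branch.* That step leads to consultation. The direct route is the step taken when symptoms resolve (cases 2 and 3).
- *That terminating the initial escalation means removal.* A child who has tolerated at least 1.5 mg protein can go on at that dose.
- *That removal is at stake only for children treated at or below 0.8 mg.* A child treated after the 1.5 mg dose may not have tolerated it either.
- *That uneven application biases the comparison of arms.* It is an inference that reactions fall almost wholly on the OIT arm. Randomization is stratified by site, site is a model covariate, and nothing shows that sites would differ.
- *That the weekday hours stated for the Chair and Co-Chair are a contradiction.* Visit 0 is scheduled and a physician must be on site.

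**Conclusion.** The concern holds for one defined situation: moderate symptoms during initial dose escalation, with more than one rescue medication or repeat antihistamine. In that situation Section 6.7.2 gives two instructions and the readable text ranks neither above the other. The point is worth correcting because it governs re-exposure of a very young child who has just been treated.

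The statistical consequence is secondary and of unknown size. It runs only through children who miss the 1.5 mg threshold and have no evaluable OFC, and their number cannot be derived. The 2- to 4-fold difference in starting dose does not last: on the Table 1 schedule it delays arrival at 2000 mg by at most 4 weeks. The conclusion assumes that Figure 2 does not already settle the order. If it does, the written paragraphs still need to be aligned with it.

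**What to change.** Reconcile the moderate-symptom branch, the medication paragraph and Figure 2 so that Section 6.7.2 states one consequence for a second medication or repeat antihistamine, and says which paragraph prevails over the symptom-grade branches. In the same edit:

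- Check consistency with Section 5.2, which separately stops further escalation for a subject with severe symptoms who receives aggressive therapy. It does not resolve the moderate case, but it should not pull in another direction.
- Clarify how a single non-antihistamine rescue medication is handled.

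Which clinical rule applies is for the protocol team to decide; no view is taken here. The cost is a few sentences in an amendment, a check of Figure 2 and of site training, and some loss of discretion in whichever paragraph is tightened. Sample size and analysis are unchanged.

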6.7.3 Build-up

After the initial dose escalation day, the participant will return to the research unit the next morning for a dose of the highest tolerated dose from the initial escalation day. This dose will be at least 3 mg peanut flour (1.5 mg peanut protein) and will be maximum 12 mg peanut flour (6 mg peanut protein). The dosing escalation will be incremental based on previous OIT studies.

The first daily dose of peanut will be given in the clinical research unit to ensure there are no ill effects of the once-daily dosing. Thereafter, the daily dose will be given at home. Every 2 weeks (12 to 21 days), the participant will return to the research unit for a dose escalation. During observed dose escalation visits, if there are no symptoms after a 30 minute-to-2 hour observation period, the subject will be discharged. The observation time period is dependent on the length of time on the study, the subject's previous dosing history for the immediate past 2 weeks and throughout the study, and number of missed doses during the past 2 weeks.

With observed dose escalations, vital signs will be performed prior to dosing, before discharge, and anytime moderate symptoms occur. Physical assessment will be performed at each of these set times and at 30 minute intervals while the subject is in the clinical research unit for dose escalations. If symptoms occur that do not require treatment, the participant will be observed until they resolve. If symptoms occur that require diphenhydramine or albuterol, the subject will be observed for a minimum of 2 hours or until the participant's symptoms resolve. If symptoms occur that require epinephrine, the participant will be observed a minimum of 4 hours or until the participant's

symptoms resolve. If symptoms do not fully resolve after 4 hours or if new symptoms occur, the participant will be transferred to a hospital and observed overnight at the physician's discretion.

Participants will be given the contact information for the study staff which includes email addresses, pager numbers, and office phone numbers for questions or concerns as they arise during the study. An on-call physician at each site will be reachable by subjects day or night. At each dose escalation visit to assess for dosing compliance and dosing reactions the contact information will be reinforced to the family. Any dose escalation attempts may be postponed for 1-2 extra weeks based on clinical judgment. An escalation attempt must be made by 4 weeks. Participants should withhold their daily home dose of study product on the escalation day but should take all other prescribed medications unless told to hold for study procedures.

The daily home dose should be taken as part of a meal. It is recommended that the dose be taken at a consistent time (within a 4-hour time period), and it is critical to take the dose every day. Doses should be separated by at least 12 hours. Participants that require dosing reduction during the 2-week period will reset their 2-week escalation schedule to maintain the new dose for a 2-week period prior to attempting to escalate again.

Participants will be allowed to take their other daily medications during the build-up and maintenance phases of the study (i.e., antihistamines, albuterol).

Participants will be free from active wheezing or a flare of atopic dermatitis prior to any dose escalation. Participants will be maintained on their current dose of study product until their flare of asthma or atopic dermatitis resolve.

Participants may develop symptoms during dosing for the build-up phase. The investigator's judgment will be required to determine the best course of action with possible actions being:

1. Continue with daily home dosing.
2. Continue the same daily dose for the rest of the 2-week interval.
3. Return for repeat dosing in the clinical research center.
4. Return for dosing of previously tolerated dose (without escalation) in the clinical research center.
5. Discontinuation of dosing.

If a participant has a dose escalation in the clinical research center without symptoms, the action should be to continue per protocol with daily home dosing of the tolerated dose with the next escalation visit to the clinical research center 2 weeks later. If the participant only experiences oral/pharyngeal pruritus during the administration of the daily dose, then the same dose can be repeated the next day at home and continued throughout the interval unless other symptoms begin to develop (see below).

For *mild symptoms*, defined as —

- skin — limited or localized hives/swelling, skin flushing or pruritus
- respiratory — rhinorrhea or sneezing, nasal congestion, occasional cough, throat discomfort
- GI — mild abdominal discomfort or minor episode of vomiting

The action should be to either repeat the dose the next day (day 2) at home or to have the participant return to the clinical research center the next day (day 2) for a repeat of the previous day's dose or the last tolerated dose (at the physician's discretion). If the dose is tolerated, then the participant will

continue on that dose and return at the normal interval. If the dose causes mild symptoms again, then the participant may return to the clinical research center (day 3) and be given the last tolerated dose or a 1-2 step dose reduction. If tolerated, the participant will continue on this dose for the normal time interval. If mild symptoms recur, a 1-2 step reduction would be administered the next day (day 4). If tolerated then that dose would be continued for 2 weeks. If not tolerated, consultation with the Protocol Chair would be indicated.

For *moderate symptoms*, defined as—

- skin — systemic hives or swelling
- respiratory — throat tightness without hoarseness, persistent cough, wheezing without dyspnea
- GI — persistent moderate abdominal pain/cramping/nausea, increased vomiting

The action should be to have the subject return to the clinical research center the next day (day 2) for dosing with the previous day's dose or the last tolerated dose under observation. If the dose is tolerated, the participant will continue on that daily home dose for the normal time interval per protocol. If the subject does not tolerate this dose, the participant should receive the last tolerated dose or a 1-2 step dose reduction (day 3) in the clinical research center or at home if the planned dose was previously tolerated. If this dose is tolerated, it will be continued as the daily home dose for the normal time interval, then escalation attempted in the clinical research center as noted below. If this dose is not tolerated, then the next dose will be a 1-2-step reduction in dosing, and the dose will be given at the clinical research center (day 4). If this next dose is not tolerated, then a discussion with the Protocol Chair or Co-Chair will ensue to make a decision about whether to continue the subject on active treatment in the study.

For more *severe symptoms*, defined as —

- respiratory — laryngeal edema, throat tightness with hoarseness, wheezing with dyspnea
- GI — significant severe abdominal pain/cramping/repetitive vomiting
- neurological — change in mental status
- circulatory — hypotension

The action should be to treat the participant, and at the physician's discretion either: (1) have them return to the clinical research center the next day (day 2) for dosing with a two-step reduction in dose under observation or (2) discontinue them from the active treatment. If the participant tolerates the dose reduction, then they will remain on that dose for 2 weeks and then return to the clinical research center for the dose escalation. A discussion with the Protocol Chair or Co-Chair may ensue to make a decision about whether to continue the subject on active treatment in the study.

For a completed dose escalation with no symptoms, participants should be observed for a minimum of 30 minutes. For mild symptoms, subjects should have a 1-2 hours post-protocol observation period. For moderate to severe symptoms, the observation period should be at least 4 hours and up to 24 hours based on symptoms and treatment regimen needed to stabilize.

If a participant fails dose escalation after 3 consecutive (with 2-4 weeks between) attempts, he or she will be considered a dose escalation failure, and the last tolerated dose will be accepted as the maintenance dose. If the participant has attained a dose of 500 mg peanut flour (250 mg peanut protein), this dose will become the maintenance daily home dose. If 500 mg peanut flour (250 mg peanut protein) has not been attained, the subject will be removed from the dosing arm and will be followed only as a longitudinal follow-up participant.

If a child reaches the 2g dose prior to visit 15 (week 28) (either at visit 13 or visit 14) per the schedule of events, there will be two scenarios.

Scenario 1) If the child reaches 2g at visit 13, the child will be dispensed 2 weeks of 2g home dosing and return for their next visit in two weeks (visit 14). If the child is tolerating 2g well, then the child will be dispensed 4 weeks of the 2g dose and visit 15 can be a telephone visit. The child must return to the clinic for visit 16 (week 30) within the protocol-specified windows (-2 to 7 days).

Scenario 2) If the child reaches the 2g dose at visit 14, the child will be dispensed 2 weeks of 2g home dosing and the child will have to come to the clinic for visit 15 and visit 16 within the protocol specified visit windows. There will be no visit 15 telephone visit with this scenario.

Participants who initially tolerated a certain dose may at some point no longer accept it. Dosing can be reduced to the next lower level. If the participant still does not accept the dose, it may be reduced again to the next lower level. If the participant still does not accept the dose, the participant will be considered a failure at Build-up.

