5.2 DISCONTINUATION OF STUDY TREATMENT

Participants will be terminated from further allergen therapy for the following reasons:

- Severe anaphylaxis with hypotension secondary to OIT dosing or any peanut food challenge.
- Inability to reach 3 mg peanut flour (1.5 mg peanut protein) during the initial dose escalation.
- Inability to reach 500 mg (250 mg peanut protein) during the Build-up phase.
- Poor control or persistent activation of secondary atopic disease (e.g., AD, asthma).
- Development of eosinophilic gastrointestinal disease.
- Circumstances (e.g., concurrent illness, such as gastroenteritis) requiring missed home dosing of > 14 consecutive days.
- Non-adherence with home dosing protocol with excessive missed days, defined as 3 occasions on which more than 3 consecutive home doses of study medication are missed.
- Eosinophilic esophagitis.
- Severe adverse event other than anaphylaxis related to investigational product.

Further care will be provided according to the judgment and practice of the site investigator.

Any subject deemed to have severe symptoms and who receives aggressive therapy at any time per investigator's discretion, should be discontinued from further escalation and followed-up as appropriate.

Participants who cease therapy should be asked to complete all assessments listed for Discontinuation Visit in Appendix 2.

If study treatment is discontinued, the DAIT/NIAID Medical Monitor will be notified.

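### Section 6.7.3 leaves next-day re-dosing and later escalation open after severe dosing symptoms, with no exception for events where Section 5.2 ends allergen therapy or escalation

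*Combined protocol and SAP*

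**What the plan says.** Section 6.7.3 defines the severe category of build-up dosing symptoms. The list covers serious respiratory and gastrointestinal symptoms and also includes "neurological — change in mental status" and "circulatory — hypotension". For the whole list the physician treats the child and then has a free choice. Option (1) is to "have them return to the clinical research center the next day (day 2) for dosing with a two-step reduction in dose under observation or" (2) to discontinue active treatment. A child who tolerates the reduced dose will "remain on that dose for 2 weeks and then return to the clinical research center for the dose escalation". Discussion with the Protocol Chair or Co-Chair is possible but not required.

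Section 6.7.4 applies the build-up symptom rules throughout maintenance. Section 6.8.1 applies them to re-escalation after missed doses.

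Section 5.2 opens with "Participants will be terminated from further allergen therapy for the following reasons". Its reasons include "Severe anaphylaxis with hypotension secondary to OIT dosing or any peanut food challenge" and "Severe adverse event other than anaphylaxis related to investigational product". A later sentence in 5.2 says that a participant with severe symptoms who receives aggressive therapy should have no further escalation.

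**The concern.** Section 6.7.3 is the instruction a physician would turn to after a reaction. It names hypotension, offers re-dosing the next day, and neither mentions Section 5.2 nor says which section prevails. A physician who follows it as written could give another peanut dose after an event for which 5.2 ends allergen therapy, or resume escalation where 5.2 says it should stop. The participants are aged 12 months to under 48 months at entry, so what is at stake is participant safety and consistent handling across sites.

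Two other parts of the protocol are stricter. Exclusion criterion 1 in Section 4.2 keeps out children who have already had severe anaphylaxis with hypotension to peanut. For severe symptoms on the initial escalation day, Section 6.7.2 stops dosing and gives no re-dosing option in that instruction.

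**Working it through.** No arithmetic applies, and the plan states no figure to reproduce. The check is to take each kind of severe dosing event and read the two sections side by side.

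| Event after a dose | Section 5.2 | Section 6.7.3 | Result |
|---|---|---|---|
| Severe anaphylaxis with hypotension | Named; allergen therapy ends | In the severe list through hypotension; option (1) open | Firm conflict on re-dosing |
| Severe symptoms treated aggressively | Should have no further escalation | Escalation resumes 2 weeks after a tolerated reduced dose | Firm conflict on re-escalation |
| Hypotension alone | Not named | Option (1) open | Conflict by inference |
| Change in mental status | Not named | Option (1) open | Conflict by inference, weaker |

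**Row 1.** The event meets a mandatory reason in 5.2 and also falls in the 6.7.3 severe list. One section ends therapy and the other leaves a day-2 dose to discretion.

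**Row 2.** The 5.2 sentence uses the same term, severe symptoms, applies at any time, and is about escalation. It does not bar a reduced dose on day 2. It is worded as 'should', leaves room for the investigator's discretion, and does not define aggressive therapy. Once a site judges it to be met, however, the route back to escalation in 6.7.3 contradicts it.

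**Row 3.** Appendix 3 says reduced blood pressure after allergen exposure makes anaphylaxis likely, and it places hypotension in the severe stage. Section 8.3.2.2 has dose-related hypotension recorded as an adverse event, and Table 3 grades it 3 (severe). Read together, these would ordinarily bring dose-related hypotension under one of the two 5.2 reasons. But 5.2 does not name hypotension on its own, cites neither Appendix 3 nor Table 3, and does not define a severe adverse event.

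**Row 4.** Table 3 grades change in mental status as 3. The 8.3.2.2 list contains confusion but not change in mental status as such, and Section 8.2.2 says dosing symptoms are not recorded as adverse events unless the 8.3.2.2 criteria are met. The event may therefore meet a 5.2 reason, but the text does not settle it.

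**Do other provisions close the gap?**
- Once a reaction is worse than mild, Section 6.7.3 sets a longer watch: "the observation period should be at least 4 hours and up to 24 hours based on symptoms and treatment regimen needed to stabilize". This delays discharge but does not rule out a dose the next day.
- The day-2 dose is given at the research center under observation. That reduces the risk but leaves the dose permitted.
- If the event is serious, Section 8.3.2.3 requires recording and notification within 24 hours. Those steps need not be complete before the day-2 dose.
- The stopping rule in Section 3.4.1 needs more than one event of systemic allergic symptoms with significant hypotension. It does not act on the first.

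None of these says that option (1) is unavailable after a first event.

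**The case against.** The strongest reply is that this is only a missing cross-reference. Section 5.2 is mandatory and narrow. Section 6.7.3 is permissive, covers a wider class of symptoms, and lists discontinuation as option (2). On an ordinary reading the narrow mandatory rule limits the general discretionary one, and no site is told to do two incompatible things.

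Much of this stands. Option (1) is never required, and choosing option (2) satisfies both sections. A reader might infer that 6.7.3 forces a breach of 5.2; it does not. What does not stand is the claim that precedence is clear. No text says that 5.2 prevails, and 6.7.3 names hypotension while expressly granting the choice.

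A second reply is that 5.2 works in tiers: some severe symptoms end escalation only, while severe anaphylaxis with hypotension ends therapy. That is correct, and it limits the point. A reader might infer that every dose-related hypotension, or every change in mental status, is already a termination event. The documents do not say so. Appendix 3 says only that anaphylaxis is likely, and 5.2 does not refer to it.

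A third reply is that the existing safeguards are enough. They narrow the gap, but none of them closes it.

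**Conclusion.** The point holds in a limited form. Section 6.7.3 as written leaves open an action that Section 5.2 rules out in one situation (re-dosing after severe anaphylaxis with hypotension) and advises against in another (re-escalation after aggressively treated severe symptoms). It is one rule with reach in three settings: build-up, the 104 weeks of maintenance, and re-escalation after missed doses. It should be fixed.

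Its size in participants is unknown, because the documents give no rate for dose-related hypotension or for the other severe events. The size of a two-step reduction could be worked out from Table 1, but it would not measure risk. A reader might also suspect an effect on the trial's results; none is claimed, because nothing here bears on an endpoint definition or an analysis.

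The first conflict rests only on the wording of the two sections. The second also depends on a site judging that aggressive therapy was given, a term that 5.2 leaves undefined.

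**What to change.** Add one sentence to the severe-symptom paragraph of Section 6.7.3: *Option (1) is not available for any event that meets a Section 5.2 reason for ending allergen therapy, and escalation does not resume where Section 5.2 says the participant should be discontinued from further escalation.* Because 6.7.4 and 6.8.1 refer back to the build-up rules, the exception then applies there as well.

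Whether hypotension alone should always end therapy is a clinical choice for the sponsor. It would be a new rule and is not part of this correction.

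The cost is a protocol wording amendment and a memo to sites, with no added procedures. Physicians lose a little discretion, but only where 5.2 already limits it.
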